A. Body Weight – scales will be purchased and provided to the patient while participating in the study. All weights will be obtained on the same scale for each patient to assure consistency of measurements. Measurements will be performed in the preoperative holding area prior to surgery, the evening of surgery on the orthopaedic floor and every morning the patient is hospitalized using the same scale assigned to that patient. Body weight measurements will be repeated at home 48 hours' post-discharge and at one and two weeks either at home or in the clinic with the same scale as previously utilized. An additional measurement will be obtained at 3 weeks postoperatively if the patient's body weight at 2 weeks has changed more than +/- 2% from their preoperative value. Funding of the cost of the scales will come out of the CJR research funding.

B. Knee Range of Motion: This will be assessed preoperatively (at their clinic appointment), on POD #1 and 2 by the research staff if the patient has not been discharged, and at 1, 2, 3 and 4 weeks postoperatively by the outpatient physical therapy office. Patient standardized forms will be provided to the outpatient physical therapists to record all post-hospital measurements. Measurements will be done with a standard goniometer.

C. Leg Anthropometric (Girth) Measurements: girth measurements will be performed at 5 & 10 cm suprapatellar, midpatella, and 10 cm infrapatellar with the use of a standard tape measure. These measurements will be collected at their pre-operative visit by research staff, POD 1 and 2 by research staff, if the patient has not been discharged and post-discharge measurements will be performed by the outpatient physical therapist at the same intervals and recorded on the same outpatient data sheet as described in item B above.

D. Transfusion: Number of transfusions will be recorded and compared between both groups. Transfusion criteria will not deviate from our normal post-operative care protocol.

E. Wound Complications: the incidence of wound infection and wound drainage will be assessed and recorded. Compressive dressings will be changed daily until wound is dry. If wound is draining at hospital discharge, the patient will be provided with home dressing supplies and instructed on how to perform daily dressing changes. The patient will take a daily photo of the wound and removed dressing daily and email it to CJR until the wound is dry. This is standard protocol for our patients currently.

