F. Thromboembolic Disease: Screening will be based on clinical assessment of the participating medical team members, which is standard protocol with all of our patients. The incidence of thromboembolic events will be recorded. All patients in the study will use aspirin 81 mg twice daily for DVT prophylaxis.

G. Muscle Strength: quadriceps strength will be assessed on POD #1 and 2 by research staff (in the hospital) and repeated at 2 and 6 weeks postoperatively at their standard of care follow-ups in the office by research staff. The strength testing will be calculated using a handheld dynamometer which is standard testing for strength in many post-operative patients currently.

H. Functional Performance Assessment: Functional tests will be performed at their preoperative appointment and once again at their 2 and 6 weeks postoperatively and will include the timed up and go (TUG) and the 30 second sit-to-stand tests. The tests will be performed in the office by research staff. These are standard tests that are often performed in physical therapy clinics to assess patient progress.

I. Length of the Hospitalization & Readmission Incidence will be recorded for both groups.

J. Postoperative Pain Assessment: Pain will be assessed using a pain VAS scale daily while hospitalized, then three times per day for 4 weeks postoperatively. Patients will be given a log to record these measurements outside of the hospital setting.

K. Adverse Events: episodes such as symptomatic hypotension (light-headedness, syncope), emesis, the need the IV fluid boluses, and other hospital and post-discharge events will be recorded.

L. Blood Pressure: this will be recorded in the Preoperative Care Unit, PACU, upon arrival to the nursing unit, and every 8 hours thereafter while hospitalized. This is standard practice for all of our patients currently.

M. PONV (Post-operative Nausea and Vomiting) - PONV will be assessed throughout their hospital stay; vital signs are checked per hospital nursing protocol, patients will be asked about Nausea: None, Mild, Moderate or Severe.

N. Patient Reported Outcome – We will be collecting the Knee Society Score(KSS) Knee injury and Osteoarthritis Outcome Score (KOOS) and the VR-12 from the patients pre-operatively as well as at their 2 week and 6 week follow up appointments. These are validated patient reported outcome measures that are already collected as standard of care at Colorado Joint Replacement.

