Based on my reading of the fluid management protocol, the study evaluates the hypothesis that the euvoolemia regimen leads to better outcomes than the traditional regimen. The former corresponds to the treatment group and the latter to the control group for the analysis, and assuming that the two groups demonstrate similarities in terms of potential pre-treatment confounding variables, such as measures obtained from preoperative history and physical, a comparison of post-treatment outcomes seems appropriate (e.g., t-tests). Even under random assignment to treatment, checks can be performed to ensure effective equivalence of confounders across treatment and control groups, an essential step in the case of small samples. If the results of such checks reveal potential confounding, including control variables in the analysis may be appropriate (e.g., in a linear regression) or a matching design to generate treatment-control pairs can be used.

While I do not have any substantive training in this field, it seems that some of the outcomes listed in the Procedures: Primary Outcomes section of the protocol may be mediated by others. For example, the association between receiving the treatment and readmission or length of hospitalization may be mediated by some of the other outcomes listed. Are there any known or suspected mediators at this point, either from the list of outcomes or beyond?

Concerning statistical power, in the figure below I calculate power (y-axis) for a range of hypothesised values of estimated effect sizes (colored lines), sample sizes per treatment and control group (x-axis), and arbitrarily chosen levels of significance (α) across the panels. Regarding α , I start with 0.05 and then make an adjustment based on an arbitrary number of hypotheses to be evaluated (eight, in this demonstration). The solid horizontal line at 0.8 represents the commonly accepted power value. As an example from Figure 1(b), for a medium-high effect size of 0.6 (green line) and evaluating eight hypotheses, in order to achieve power of 0.8 would require approximately 65 participants in each of the treatment and control groups.

[figure not shown]

Figure 1: Power calculations for hypothetical effect sizes and sample sizes (per group) at given values of α . The left panel uses $\alpha = 0.05$ and the right panel employs a Bonferroni correction for multiple hypotheses. In this case, evaluating eight hypotheses with a desired α of 0.05 yields an adjusted α of 0.00625.

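### Quadriceps strength has no scheduled preoperative value and is compared unadjusted by default, so the comparison gives up precision that prespecified baseline adjustment could recover

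*Combined protocol and SAP*

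**What the plan says.** All references are to the combined protocol and SAP.

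- **Strength (section 2, Primary Outcomes, item G).** In hospital, "quadriceps strength will be assessed on POD #1 and 2 by research staff (in the hospital"). It is then "repeated at 2 and 6 weeks postoperatively at their standard of care follow-ups in the office by research staff". All four time points follow surgery.
- **TUG and 30-second sit-to-stand (item H).** "Functional tests will be performed at their preoperative appointment and once again at their 2 and 6 weeks postoperatively", and "The tests will be performed in the office by research staff".
- **Range of motion (item B).** "This will be assessed preoperatively (at their clinic appointment), on POD #1 and 2 by the research staff".
- **Girth (item C).** "These measurements will be collected at their pre-operative visit by research staff".
- **Patient-reported scores (item N) and bioimpedance (item Q).** Each has a preoperative value.
- **Analysis (section 9, Methods of Evaluation).** If the groups look alike before treatment, "a comparison of post-treatment outcomes seems appropriate (e.g., t-tests"). Control variables or matching come in only if balance checks point to confounding.

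**The concern.** Strength is listed under Primary Outcomes, and patient function is named as a primary outcome in sections 1, 3 and 4. It is the only functional measure without a scheduled preoperative value, and no reason is given. Eligibility covers ages 18 to 75 and BMI 19 to 38, so wide variation in strength between patients is plausible. Under an unadjusted t-test all of that variation stays in the error term.

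Three things are at stake: the precision of the strength comparison, the ability to check balance on preoperative strength itself, and the ability to report change from preoperative strength. The POD 1 value cannot serve as the baseline, because it is taken after the fluid regimens have begun to differ.

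**Working it through.** **Inputs from section 9.** Effect size d = 0.6 SD; eight hypotheses, so alpha = 0.05/8 = 0.00625; target power 0.8; about 65 per group. Sidedness is not stated, although the hypothesis is worded directionally.

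**Assumed input.** r, the correlation of preoperative with later strength. The documents give none, so 0.3, 0.5 and 0.7 are used as a range.

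**Step 1: reproduce the plan's figure.** Two-sample comparison of means, 1:1 allocation, no covariate:

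| Test | n per group for 80% power | Power at 65 |
|---|---|---|
| One-sided t | 64 | 0.811 |
| One-sided normal | 62 | 0.822 |
| Two-sided normal | 72 | 0.754 |
| Two-sided t | 73 | 0.738 |

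The one-sided t-test reproduces the stated 65. Both readings are carried forward, since the plan does not choose.

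**Step 2: effect of adjusting for a strength baseline.** ANCOVA multiplies residual variance by 1 − r² and the standard error by √(1 − r²). The equivalent unadjusted sample is 65/(1 − r²) per arm. Power comes from the noncentral t with noncentrality [0.6/√(1 − r²)] × √(65/2). Degrees of freedom are 2 × 65 − 2 = 128 unadjusted and 127 with one covariate.

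| r | Variance cut | Noncentrality | Equivalent n per arm | Power, one-sided | Power, two-sided |
|---|---|---|---|---|---|
| none | 0% | 3.42 | 65 | 0.811 | 0.738 |
| 0.3 | 9% | 3.59 | 71.4 | 0.852 | 0.788 |
| 0.5 | 25% | 3.95 | 86.7 | 0.920 | 0.876 |
| 0.7 | 49% | 4.79 | 127.5 | 0.987 | 0.976 |

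**Step 3: effect of adjusting for TUG and sit-to-stand instead.** The same variance factor applies, with r replaced by the multiple correlation R of the two tests with later strength; one further degree of freedom is lost. The documents give no R. It may well be below the correlation of strength with itself, so the rows above should not be read as the gain from this route.

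**Step 4: size of chance imbalance.** With 65 per arm, the difference between arms in mean preoperative strength has standard error √(2/65) = 0.175 SD. A gap above 0.2 SD in either direction corresponds to z = 0.2/0.175 = 1.14, which occurs in about 25% of randomisations.

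**The case against.** The strongest reply is that this is an optional gain in efficiency and not an error. Much of that stands.

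- **Bias.** A reader might infer that the missing baseline biases the strength result. It does not: allocation is random, and the unadjusted comparison is valid.
- **Imbalance.** A reader might infer that chance imbalance cannot be removed. It can be removed in part. Age, BMI, body weight, TUG, sit-to-stand and bioimpedance are available before surgery, and section 9 allows control variables. Only imbalance in strength that these do not explain is out of reach.
- **Uniqueness.** A reader might infer that strength alone loses precision. Section 9's default t-tests also leave the baselines of range of motion, girth, TUG and sit-to-stand unused. A strength baseline would change nothing unless that rule changes too. Nor is strength the only primary outcome without a preoperative value: pain VAS (item J) has none scheduled either.
- **Underpowering.** A reader might take 0.74 as the plan's own power for strength. The plan states 0.8, and the one-sided reading meets it. Section 9 also offers 0.6 SD and eight hypotheses as an illustration, not as a target for strength.
- **Comparator.** The gains in the table are against no adjustment at all. The extra gain of a dynamometer baseline over the existing covariates is smaller and cannot be estimated from the documents.
- **Attachments.** The Patient Data Log is not shown, so a preoperative strength field there cannot be excluded. The protocol text schedules none.

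What survives is that precision is given up without a stated reason, and that part of it can be recovered with data already planned.

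**Conclusion.** The point holds as a minor improvement. Strength has no scheduled preoperative value, the default analysis is unadjusted, and the comparison is unbiased but less precise than it could be. For an assumed r of 0.3 to 0.7, the residual variance that a strength baseline would remove is 9% to 49%: modest at the low end, substantial at 0.5 and above.

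This rests on a single r applied to all time points and on 65 patients per arm contributing. Any correlation may be lower on POD 1 and 2, shortly after surgery and a nerve block, than at weeks 2 and 6. POD 2 numbers may also fall short, because section 2 anticipates some discharges on POD 1.

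**What to change.** **At no cost.** State in section 9 that strength at each time point will be compared by ANCOVA, with treatment group, preoperative 30-second sit-to-stand and preoperative TUG in the model, whatever the balance checks show. Both tests are already collected under item H.

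**Optional, at small cost.** In item G, add a handheld-dynamometer reading of the operative leg at the preoperative appointment, where research staff already run TUG and sit-to-stand, and use it as the ANCOVA covariate. The device and staff are those already used for the later strength tests. The cost is a short extra test per patient and one more exposure to the testing risks in section 5: commonly soreness for about 2 days, less commonly strains or tears. Adding the reading without prespecifying the adjustment would not deliver the gain.

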***Traditional Intravenous Fluid versus Oral Fluid Administration in Primary
Total Knee Arthroplasty: A Randomized Trial***

Version 8.0 July 6th, 2017 - NCT03719378

Traditional Intravenous Fluid versus Oral Fluid Administration in Primary Total Knee Arthroplasty: A Randomized Trial

1. Purpose: Evidence-based guidelines on optimal perioperative fluid management have not been established in patients undergoing orthopaedic surgery. Typical intraoperative and post-operative fluid management has been arbitrary without evidence based guidelines established following total joint replacement. We have observed many patients post-operatively with side effects such as fluid overload leading to medical complications requiring either prolonged hospitalization or readmission. Additionally, this overload may lead to wound healing complications secondary to fluid shifts which may be devastating in this patient population. Recent randomized trials in major abdominal surgery suggest that large amounts of IV fluid may increase morbidity and hospital stay. Additionally, this increase fluid may be detrimental in patients with anastomosis leading to failure and/or complications in this patient population. We have defined to specific groups of interest to study in this patient population with regards to fluid management. The first group is the “traditional” IV fluid group where the anesthesiologist gives an unspecific amount of fluid intraoperatively and post-operatively the patient gets a set amount of fluid based on “protocol” on the orthopaedic floor (i.e. 75 cc/hour until good oral intake). This is the protocol utilized by most orthopaedic practices throughout the United States. The second group is defined as patients who are given a specific protocol preoperatively to optimize hydration, followed by limited fluids intraoperatively based on physiologic parameters. This study will investigate the effects of two regimens of intraoperative fluid management (“traditional” vs. “oral”) with physiologic and patient function as primary outcome measures after surgery.

2. Procedures:

- Patients meeting the inclusion criteria who are schedule for unilateral primary TKA will be identified.
- The patients will be approached regarding the study (in clinic by research staff) and if the patient is agreeable, informed consent will be obtained.

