O. Pressors – We will be collection the total amount of any pressor drugs (e.g. Ephedrine and Phenylephrine) given intra-operatively and in PACU in both groups.

P. Oral Fluid Intake Log – The patients that are in the Oral group will have an additional page to keep track of their fluid intake prior to surgery.

Q. Bioimpedance machine - This will be used to track patients body composition before and after surgery. Research staff in the office will collect this information at the patient's pre-op visit, POD#1 and 2 as well as their 2 week and 6 week visit.

R. Body Temp – The patient's body temp will be recorded pre-operatively as well as in the recovery room.

S. Time from their last clear fluid drink to the start of anesthesia, this start up time will be recorded for both groups.

T. Patient perception/satisfaction with their fluid protocol.

Patient Withdrawal: subjects may withdraw from the study for any reason at any time. Should a subject decide to withdraw from the study, all data collected up to that point will be deleted and not used for statistical analysis. Withdrawal from the study will not affect the patient's treatment after their total knee arthroplasty.

3. Scientific Background of the Study – As stated in the “purpose” section –

Evidence-based guidelines on optimal perioperative fluid management have not been established in patients undergoing orthopaedic surgery. Recent randomized trials in major abdominal surgery suggest that large amounts of fluid may increase morbidity and hospital stay. This study will investigate the effects of two regimens of intraoperative fluid management (“traditional” vs. “oral”) with physiologic and patient function as primary outcome measures after surgery.

4. Specific Aims of the Study – This study will investigate the effects of two regimens of intraoperative fluid management (“traditional” vs. “oral”) with physiologic and patient function as primary outcome measures after surgery.

5. Description of risks and measures to minimize risks.

- All patients, regardless of their volume protocol (traditional vs. oral), will follow a traditional post-operative course which includes daily labs and monitoring physiologic status from both the orthopaedic and general medicine team.
- All patients will have traditional post-operative follow-up care which will not be varied.

Surgical Risks:

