10. Trial Design

- Please refer to the above sections regarding the discussion of the research study
- Patients will be identified based on the inclusion and exclusion criteria stated above. The patients will then be randomized into the “traditional” vs. oral arms of the study. Outside of the amount of preoperative, intraoperative and postoperative fluids given to the patients, there is no difference in the treatment or outcome measures between the 2 groups.

11. Statistical calculations- please refer to section 10, methods of evaluation

12. Confidentiality of the data.

- Data will be collected on a password protected excel spreadsheet that will be stored on a Centura password protected computer.
- All data collected will be de-identified.

Data sharing.

With whom will *identifiable* (contains any of the 18 identifiers) data be shared outside the immediate research team? For all that apply, explain confidentiality measures. Include data use agreements, if any.

Data will be shared with:		Name/Description/s
	No one	
	Coordinating Center	
	Statisticians	
x	Other researchers	[name]; [name]; [name]; [name], , [name], [name] (research coordinator), [name] (research data entry clerk), [name] (clinical research associate).
	Registries	
	Sponsor/s	
	External labs for additional testing	
	Journals	
	Publicly available dataset	
	Other	

Data security for storage and transmission. Include all that apply.

For electronic data stored on a desk top computer:

 Secure network	 Password access	 Data encryption	 Password protected file(s)
 Other comparable safeguard (describe):		Data will be de-identified	

For portable computing devices/external storage devices (e.g. laptop computer, PDA, CDs, memory sticks):

 Power-on password	 Data encryption
 Automatic log-off	 Password protected file(s)
 Other comparable safeguard (describe): Data will be de-identified	

For hardcopy data (including human biological specimens, CDs, tapes, etc.):

 Data de-identified by research team (stripped of the 18 identifiers)	 Locked suite or office

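### Strength, TUG and sit-to-stand at weeks 2 and 6 are tested by research staff, and nothing in the plan keeps the treatment arm from them

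*Combined protocol and SAP*

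**What the plan says.** Section 2 places five assessor-dependent measures under Primary Outcomes: range of motion by goniometer (item B), girth by tape (item C), quadriceps strength by handheld dynamometer (item G), and TUG and sit-to-stand (item H).

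- **Strength:** "quadriceps strength will be assessed on POD #1 and 2 by research staff (in the hospital"), and research staff repeat it in the office at weeks 2 and 6.
- **TUG and sit-to-stand:** before surgery and at weeks 2 and 6. "The tests will be performed in the office by research staff".
- **Range of motion:** research staff on postoperative days (POD) 1 and 2 for patients still in hospital, then "at 1, 2, 3 and 4 weeks postoperatively by the outpatient physical therapy office".
- **Girth:** research staff on the same inpatient days, after which "post-discharge measurements will be performed by the outpatient physical therapist at the same intervals". For both measures, "Patient standardized forms will be provided to the outpatient physical therapists to record all post-hospital measurements".

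Research staff also recruit: "The patients will be approached regarding the study (in clinic by research staff"). Sealed envelopes govern assignment. Oral-arm patients "will have an additional page to keep track of their fluid intake prior to surgery" (item P), and item T collects patients' perception of their fluid protocol. Nothing in the document describes masking of anyone, or any step that withholds the arm from an assessor after randomisation.

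**The concern.** Patients cannot be blinded to whether they drink to a schedule or receive litres of intravenous fluid, so concealing the arm from the assessor is the main protection left for these tests. Dynamometer placement, the start and stop of a timed walk, the counting of a repetition and the amount of encouragement can all shift a result without anyone intending it.

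The staff category that tests strength and function at weeks 2 and 6 is also the one at the bedside on POD 1 and 2. If assessors who know the arm lean towards one regimen, the shift goes straight into the group difference. A larger sample does not dilute it, and it cannot be removed once the data are collected.

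**Working it through.** **1. Who could learn the arm from the plan as written**

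| Measure | Assessor and time | Exposure to the arm shown in the text | Safeguard stated |
|---|---|---|---|
| Strength | Research staff, POD 1–2, weeks 2 and 6 | Bedside contact on POD 1–2 by the same staff category | None |
| TUG, sit-to-stand | Research staff, weeks 2 and 6 | As above, through the shared staff category | None |
| Range of motion and girth, inpatient | Research staff, POD 1–2 | Bedside contact | None |
| Range of motion and girth, weeks 1–4 | Outpatient therapist | None shown | None |

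The bedside contrast comes from the two fluid protocols in Section 2. The traditional arm is due 1500 ml intravenously in the inpatient room, completing 4 litres within 24 hours. The oral arm has its line locked in the recovery unit, a 500 ml cap and a 3-day drinking schedule. On POD 1 both regimens may be visible. By POD 2 the 24-hour intravenous period should have ended, but the oral schedule is still running.

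**2. The plan's own figure**

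Inputs from Section 9: standardised effect 0.6, eight hypotheses, power 0.8, t-test, about 65 per group. Adjusted alpha: 0.05 / 8 = 0.00625.

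- Two-sided t-test: 73 per group needed; power at 65 is 73.8%.
- One-sided t-test: 64 per group needed; power at 65 is 81.1%.

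So 65 reproduces only as a one-sided t-test. Section 9 does not state sidedness, so both readings are carried below.

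**3. Effect of an assessor shift**

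Assumption: no true effect, and a systematic between-arm assessor error of b SD. The documents give no b, so it is shown as a range.

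With n = 65 per arm, df = 2 × 65 − 2 = 128 and noncentrality = b × √(n/2) = b × √32.5 = 5.70 b, which is 0.57, 1.14 and 1.71 for b = 0.1, 0.2 and 0.3. The two-sided critical values are 1.979 (alpha 0.05) and 2.780 (alpha 0.00625). Multiplied by √(2/65) = 0.1754, they give the smallest significant observed differences: 0.35 SD and 0.49 SD.

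The rejection probability is the sum of the two tails of the noncentral t. For b = 0.2 at alpha 0.05 it is 0.2037 + 0.0010 = 0.2047.

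| b (SD) | Two-sided, 0.05 | Two-sided, 0.00625 | One-sided, 0.05 | One-sided, 0.00625 |
|---|---|---|---|---|
| 0 | 5.0% | 0.625% | 5.0% | 0.625% |
| 0.1 | 8.7% | 1.5% | 14.1% | 2.7% |
| 0.2 | 20.5% | 5.4% | 30.5% | 8.5% |
| 0.3 | 39.7% | 14.7% | 52.2% | 20.9% |

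The one-sided columns assume that the shift lies in the tested direction. These are rates for a single outcome. At the enrolment target of 75 per arm, b = 0.2 gives 22.9% (alpha 0.05) and 6.4% (alpha 0.00625), two-sided, so more patients make it slightly worse.

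**The case against.** The strongest reply is that the text shows silence, not exposure, and that several tempting inferences go too far.

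- **Therapists know the arm.** A reader might infer this because they measure two primary outcomes. Nothing says so, and the therapy log is an attachment not shown, so it may already be free of allocation. What stands is that no safeguard is written down.
- **Recruiting reveals the arm.** It does not. Approach and consent precede randomisation, and the plan does not say who opens the envelope. Research staff is also a category, not one person.
- **The oral log unmasks later testers.** It covers intake before surgery only, and nothing says that it reaches an assessor at week 2 or 6.
- **The team expects the oral arm to win.** Section 9 does frame the hypothesis that way, but as its author's own reading, with a disclaimer of training in the field. Section 6 lists potential benefits for the oral arm, yet says it is unknown whether the protocols will differ.
- **The bias size is assumed.** This is right. The top value, 0.3 SD, is half the planned effect of 0.6, and one shift would not apply alike to every instrument.
- **Staffing is not shown.** The research coordinator, data entry clerk and clinical research associate appear in the data-sharing table of Section 12, which does not establish who is trained or free to test patients.

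These points narrow the concern. They do not answer the bedside contact on POD 1 and 2 or the absence of any step to separate it from the later tests.

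**Conclusion.** The concern holds for strength, TUG and sit-to-stand at weeks 2 and 6. These are assessor-dependent primary outcomes, tested by a staff category with stated inpatient contact, and nothing conceals the arm. For therapist-measured range of motion and girth it holds only as a missing safeguard.

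The size is illustrative. A 0.2 SD shift would make a false finding about four times as likely at alpha 0.05 (20.5 / 5 = 4.1) and about nine times at 0.00625 (5.4 / 0.625 = 8.6), though at the stricter level the chance for one outcome stays near 5%. Section 9 calls its count of eight hypotheses arbitrary, so that level is not a committed protection. The figures rest on an assumed shift, no true effect, 65 per arm and a t-test.

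A reader might infer that a positive functional result would be uninterpretable now and clean after masking. Neither follows. The documents do not show that bias will occur. Masking assessors would leave unblinded patients' own expectations acting on effort-dependent tests, so nominal error rates could not be assumed. The change is worth making because it removes an avoidable route for bias; its absence does not invalidate the trial.

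**What to change.** Add to Section 2:

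1. The physical therapy log carries no allocation, and outpatient therapists are not told the arm.
2. Where existing staffing allows, week 2 and 6 strength, TUG and sit-to-stand are done by a team member who did not open that patient's envelope, handle the fluid protocol or do the POD 1–2 tests, using a standard script for instructions and encouragement.
3. The oral intake log and the item T question are handled by someone else, or after testing is finished.
4. Patients are asked not to disclose their arm to testers or therapists.
5. POD 1–2 measures, and any visit at which the assessor knew the arm, are recorded and reported as unmasked.

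State as a limitation that patients' own expectations may still affect the effort-dependent tests.

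The cost is scheduling effort, a short script and a check of the forms. Some patients will disclose their arm regardless. No patients, visits or equipment are added, and treatment and sample size are unchanged.
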